**Objectives:**

Specific Aim 1. Evaluate the frequency and clinical features of the metabolic syndrome in childhood cancer survivors.

Hypothesis 1A: Components of the metabolic syndrome are realized in children and adolescents at all stages of therapy of leukemia and lymphomas, can influence the development of complications and late toxic effects.

Hypothesis 1B: Initial health conditions (abnormal IBM, family history, comorbid diseases); drug's toxicity could influence to the appearance of early manifestation of metabolic syndrome.

Specific Aim 2: Evaluate the contribution of functional polymorphisms in candidate genes to metabolic syndrome outcomes among childhood cancer patients.

Hypothesis 2A: Genetic polymorphisms involved in the regulation of the insulin resistance and cancer medications during treatment contribute to the development of metabolic syndrome in childhood cancer survivors.

Specific Aim 3: Assess the extent to which genetic predictors, doses of drugs, risk factors improve the discriminatory performance of standard clinical prediction models for metabolic syndrome outcomes among childhood cancer survivors.

Hypothesis 3 A: Development of metabolic syndrome in cancer patients depends of genetic determinants and toxic effects of antitumor therapy.

Secondary Aim 1: Assess the definition of metabolic syndrome in cohort of patients of leukemia and lymphoma and survivors.

Hypothesis 1A: Episodes of triglyceridemic, insulin resistance (Hyperglycemia, HOMA $>2,7$ , Steroid Diabetes) during the treatment could be the base evidence marker of Metabolic Syndrome in patients treated by antitumor therapy.

Hypothesis 1 B: Endothelial dysfunction as a clinical component of metabolic syndrome is responsible for cardio-vascular abnormalities in cancer survivors.

**Exploratory aim 1:** Assess the association of biomarkers and genetic predictors among childhood cancer survivors with therapeutic exposures (chemotherapy and/or radiation therapy) and metabolic syndrome.

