**Evaluation:**

Eligible persons who consent to participate in this trial will be asked to do the following:

- Vital sign measurement including resting heart rate, blood pressure, height, and weight.
- A total of 12 mL of blood will be collected in 3 test tubes. Biomarker analysis will be completed by Laboratory of Dmitry Rogachev National Medical Research Center.
- A Total of 4 mL of blood in 1 test tube will be used for genotyping for the presence of polymorphic variants in genes involved in biotransformation of xenobiotics, insulin resistance and carbohydrate metabolism in the biomolecular laboratory of Dmitry Rogachev National Medical Research Center.
- An echocardiogram and ultrasound will be performed to assess cardiac function.
- CAVI and ABI pulse wave velocity will be non-invasively measured by using the SphygmoCor VaSera VS-1500N. Arterial pressure waveforms will be recorded with a strain gauge pressure sensor placed lightly over the radial artery before and after “6-minutes physical activity”.

**Study Design:** Longitudinal

**Sample Size:** Aims of this study will be accomplished using a longitudinal assessment of 400 patients with ALL/NHL from Dmitry Rogachev National Medical Research Center and other Regional Clinics will be recruiting to the cohort at the start of the therapy MB-ALL/ BFM-NHL. Potentially 2100 survivors ALL/NHL will be treating in “Russkoe Pole” 2018-2021.

**Cases:** Participants for this study will be patients of “Russkoe Pole” cohort (RPC), a longitudinal study designed to evaluate health among children and adolescents survivors of childhood leukemia and lymphoma as they age. Participants in RPC undergo risk-based medical screening according to the Standards of Medical Insurance for rehabilitation of Cancer treated patients. Cases will be stratified by survival time (1-4, 5-9, and  $\geq$  10years).

To be eligible for RPC, cancer survivors must have been treated in Russian children oncology clinics by MB-ALL/ BFM-NHL and be 15 years of age or younger, and at least 6 months from the completion of the therapy. All the patients will have exhaustively full epicrisis of medical history with cumulative doses of medications. Because RPC is a retrospective cohort study with ongoing recruitment (additional survivors become eligible over time).

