**Study Population:**

Eligibility criteria:

- Cancer survivors:
- Treatment with chemotherapy and/or radiation therapy for a primary ALL/NHL diagnosed prior to age 17 years.
- $\leq$  15 years of age at time of enrollment.
- No cytostatic drugs uptake during the study.

Exclusion criteria:

- Diagnosis of diabetes mellitus types 1 or 2 types before antitumor therapy
- Active oncological disease
- History of allogeneic hematopoietic cell transplant
- Absence of written consent for participation from the patient or legally authorized representative

Randomization: N/A
Anticipated Primary Objective Completion Date: 10/09/2018
Anticipated Study Completion Date: 10/12/2021
Analysis of objectives: Aims 1 and 2: Descriptive statistics will be used to summarize prior cancer therapy, collected from formal medical record abstraction. Epidemiological, clinical and laboratory variables, including genetic variants will be tested for their association with metabolic syndrome. McNemar's test for paired data will be used to compare the unmatched general characteristics of cases and controls. Allele frequencies will be estimated by two-side Fisher exact test, and the Chi-square test will be used to check for departures from Hardy-Weinberg equilibrium. Aim 3: The crude disease-exposure association will be determined by estimating the OR and its 95% confidence interval (CI). This will be done by univariate conditional logistic regression, to account for the matched design. The significance of the OR will be assessed by the Wald test. Exposures for which the P-value is less than 0.25 in univariate analysis will be entered into a multivariate conditional logistic regression model. Backward stepwise regression procedures will be used to develop the final multivariate model and possible interactions will be examined. The fit of the model will be assessed by the logistic regression diagnostics procedure. Haplotypes will be constructed where applicable, and pathway analysis will be used to construct multilocus genotypic groups, rather than a "one-gene-at-a-time" approach, where possible. Exploratory Aim: The multiple regression approach as described above (plan for primary Aims 1 and 2) will be implemented to assess the relationship between biomarker levels (HOMA index, triglyceridemic) and endothelial dysfunction (rigidness of arteries and positive biomarkers) with metabolic syndrome in cancer treated patients.

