## Appendix 1 Genetic testing

The table summarizes specific polymorphisms that are candidate genes underlying genetic risk factors for metabolic syndrome after childhood cancer.

- i) A candidate gene approach, rather than genome-wide polymorphism detection, will be used,
- ii) Functional polymorphisms will be targeted, and
- iii) Genes will be identified by virtue of the fact that they have been associated with metabolic syndrome outcomes in adults, or with similar "de novo" diseases, or they are likely to affect the pharmacogenetics or pharmacodynamics of the most important drug-related risk factors for the adverse event.

Gene	SNP ID	Protein's function
INSR	rs2059806	The insulin receptor gene is a member of insulin signal transduction pathway which regulates the absorption and release of glucose, synthesis and storage of carbohydrates, lipids and protein. Mutations in the gene are associated with autosome-recessive hereditary syndromes, such as syndrome Donohue (leprechaunism) and Rabson-Mendenhall syndrome. It is possible that the heterozygote carriers of the mutations associated with these syndromes have hereditary predisposition to a metabolic syndrome.
	rs1051691	
	rs52800171	
IRS1	rs2943641	Binding of insulin to its receptor induces phosphorylation of the cytosolic substrates IRS1 and IRS2. The insulin receptor substrate 1 gene ( IRS1 ) variants ( rs2972146, rs2943641, and rs2943634) are related to body fat percentage (BF%) and multiple metabolic traits.
PPARG	rs1801282	The protein PPAR-gamma is the regulator of adipocytes differentiation.
KCNJ11	rs5219	The protein KCNJ11 is a part of ATP-dependent K + channels of pancreatic beta cells, which play a key role in insulin secretion. As a result of 67A>G nucleotide change, the lysine in the position 23 is replaced with glutamine (Lys23Gln). The change in protein structure interferes with closing of channels and leads to decrease in insulin secretion from beta cells and to violation of blood sugar level control.

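### The Wald P behind the 0.25 entry rule for the Aim 3 model drops any exposure whose discordant matched sets all lie on one side, however strong the evidence

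*Protocol*

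**What the plan says.** The relevant text is the Aim 3 part of the Analysis of objectives entry, under Study Population in the Protocol. On the crude odds ratio it says: "This will be done by univariate conditional logistic regression, to account for the matched design". The test is then fixed: "The significance of the OR will be assessed by the Wald test". The entry rule follows: "Exposures for which the P-value is less than 0.25 in univariate analysis will be entered into a multivariate conditional logistic regression model". Backward stepwise selection works on whatever has passed that rule. No likelihood-ratio, score, exact or penalised alternative is named for sparse data.

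Genetic variants are among the exposures concerned, since Specific Aim 3 under Objectives is to "Assess the extent to which genetic predictors, doses of drugs, risk factors improve the discriminatory performance of standard clinical prediction models". The Sample Size entry under Evaluation gives 400 prospectively followed patients and potentially 2100 survivors. The protocol gives no allele frequency, number of cases or matching ratio.

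Two other tests in the same entry, under Aims 1 and 2, bear on the point: "Allele frequencies will be estimated by two-side Fisher exact test" and "the Chi-square test will be used to check for departures from Hardy-Weinberg equilibrium".

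**The concern.** In a conditional logistic model only discordant matched sets carry information. If the exposed child is the case in all of them (or the control in all of them), the data are separated. The likelihood keeps rising as the log odds ratio grows, so there is no finite estimate. The Wald statistic divides the estimate by its standard error, and the standard error grows much faster than the estimate, so the statistic goes to zero and P goes to 1. The test thus gives its weakest verdict when the discordant sets agree completely.

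Here that P is more than a summary, because it decides whether an exposure is considered in the multivariable model at all. A predictor lost at this step cannot contribute to the discrimination that Aim 3 is meant to assess, and its Wald confidence interval is unusable.

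**Working it through.** The protocol states no figure to reproduce on this point. The test, model and 0.25 limit come from the Aim 3 text. The numbers of pairs, allele frequencies and true odds ratios below are assumptions.

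**1. Wald P under separation (1:1 pairs).** With d discordant pairs, all on the case side, and log odds ratio β, the log-likelihood is −d·ln(1 + e^−β). The information is d·π(1 − π), with π = 1/(1 + e^−β). Hence

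Wald z = β·√[d·π(1 − π)], which tends to 0 as β grows.

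For d = 6, Newton iteration gives:

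| Newton steps | β | SE | Wald P |
|---|---|---|---|
| 8 | 9.20 | 40.7 | 0.82 |
| 10 | 11.20 | 110.6 | 0.92 |
| 15 | 16.20 | 1,347 | 0.99 |
| 20 | 21.20 | 16,409 | 0.999 |

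For d = 5 the P-values at the same steps are 0.84, 0.93, 0.99 and 0.999. For d = 11 they are 0.76, 0.89, 0.99 and 0.999. A packaged conditional-logit routine that stops early gives 0.70 (d = 5) and 0.69 (d = 11). With 1:2 to 1:4 matching, P is 0.999 at 20 steps. Across all fits, including up to 20 pairs, P runs from 0.68 to 1.00 and never approaches 0.25.

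**2. Other tests on the same separated data.** The likelihood-ratio statistic is 2d·ln 2 on 1 df, the score statistic is d on 1 df, and the exact two-sided P is 2 × 0.5^d.

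| d (all on case side) | Likelihood-ratio P | Score P | Exact P |
|---|---|---|---|
| 1 | 0.239 | 0.32 | 1.00 |
| 3 | 0.041 | 0.083 | 0.25 |
| 4 | 0.019 | 0.046 | 0.125 |
| 5 | 0.0085 | 0.025 | 0.0625 |
| 6 | 0.0039 | 0.014 | 0.031 |
| 11 | 0.00009 | 0.0009 | 0.00098 |

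From d = 4 upward all three pass the 0.25 rule, while the Wald test fails it.

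**3. Small numbers without separation.** With b case-side and c control-side pairs, both above zero, z = ln(b/c)/√(1/b + 1/c). For 4 versus 1, z = 1.386/1.118 = 1.24 and P = 0.21. For 5 versus 1, P = 0.14; for 11 versus 1, P = 0.022. All pass. The trigger is separation, not a low carrier count in itself.

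**4. How often a real signal would be lost.** Assume 60 1:1 pairs with independent exposure within a pair, allele frequency q among controls, and carriers against non-carriers:

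- p0 = 1 − (1 − q)² and p1 = OR·p0/(1 − p0 + OR·p0)
- case-side discordance: p10 = p1(1 − p0)
- control-side discordance: p01 = p0(1 − p1)

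The harmful event is at least 4 discordant pairs, all on the case side:

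P = Σ (b = 4 to 60) C(60, b)·p10^b·(1 − p10 − p01)^(60 − b).

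Example: q = 1% and OR 5 give p0 = 0.0199, p1 = 0.0922, p10 = 0.0903, p01 = 0.0181 and P = 0.27.

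| Allele frequency | OR 1 | OR 2 | OR 3 | OR 5 |
|---|---|---|---|---|
| 1% | 0.01 | 0.06 | 0.15 | 0.27 |
| 2% | 0.02 | 0.07 | 0.11 | 0.13 |
| 5% | 0.003 | 0.007 | 0.01 | 0.02 |

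**The case against.** **Rare variants are not documented.** The protocol gives no allele frequencies, so nothing shows that any listed SNP is uncommon. The nearest remark, in Appendix 1 on the insulin receptor gene, is "It is possible that the heterozygote carriers of the mutations associated with these syndromes have hereditary predisposition to a metabolic syndrome". It concerns syndrome mutations and is not said to describe the listed SNPs. This stands: the frequency of the problem in this study cannot be judged.

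**The signal may be visible elsewhere.** Alleles are also tested with Fisher's test under Aims 1 and 2, grouping genotypes may pool sparse variants, and a statistical analysis plan might add a fallback. This mitigates in part, but none of it changes the Aim 3 entry rule, and it is the protocol itself that fixes the Wald test.

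**Stronger readings that a reader might infer, and why they fail:**

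- *Few carriers alone break the test.* They do not; 4 versus 1 pairs passes.
- *The plan contradicts itself because Fisher's test would give P below 0.001.* That needs an assumed unmatched table. With 400 children, 60 of them cases, and 5 carriers all cases, Fisher P is 0.00007. With equal numbers of cases and controls, 5 carriers give 0.062, and 11 are needed to go below 0.001. The test also compares alleles, ignores matching and serves other aims.
- *Strong effects are systematically lost.* Under the 60-pair assumption, the chance of any non-finite odds ratio is 0.34 to 0.52 at 1% allele frequency. That counts sets with no or hardly any discordance and separation in the wrong direction, and the 0.52 is the null case. The harmful event has probability 0.01 to 0.27.
- *The chi-square Hardy-Weinberg check would discard sound SNPs.* The chi-square P can be far too small in sparse data, but no rule in the protocol excludes a SNP on this check.

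**The likelihood-ratio test has its own weakness.** It is liberal in very sparse data: a single discordant pair gives P = 0.239 and would pass. At 3 pairs it enters the exposure (0.041), whereas the exact P of 0.25 does not fall below the limit. This stands and shapes the fix.

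**Conclusion.** The concern holds as a defect of the stated rule. Under separation the Wald P (0.68 to 1.00) always fails the 0.25 limit, while the matched likelihood-ratio P is 0.0085 at 5 pairs and 0.004 at 6. The mechanism does not depend on the matching ratio (1:1 to 1:4 checked) or on the software's stopping rule.

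Its practical size is uncertain. It rests on an assumed 60 1:1 pairs and assumed allele frequencies: material for uncommon exposures with large effects (up to 0.27 at 1% and 0.13 at 2%), and negligible at 5% and above (at most 0.02). It is worth correcting because the rule fails in a known way and the correction is easy. It is not grounds for saying that the Aim 3 results as a whole would be unreliable.

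**What to change.** In the Aim 3 text, replace the Wald sentence along these lines: odds ratios will be tested by the conditional likelihood-ratio test and reported with profile-likelihood 95% confidence intervals; the same P-value decides entry at 0.25; where the odds ratio is not finite, or only a few matched sets are discordant, the estimate, interval and entry P will come from a Firth-penalised or exact conditional analysis.

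Name one of those two methods, and the number of discordant sets below which it applies, before the data are seen, because different tests can decide differently at very low counts. The second clause also keeps near-empty exposures from passing on the likelihood-ratio P alone.

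The cost is a change of wording and standard software options, plus that one prior choice. Results for common exposures should hardly change. Replacing the chi-square Hardy-Weinberg check by the exact test is an optional minor improvement.

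### Aim 3 asks how much new predictors improve discrimination over standard clinical models, but the Aim 3 analysis only estimates associations

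*Protocol*

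**What the plan says.** The Objectives section of the protocol states Specific Aim 3 as: "Assess the extent to which genetic predictors, doses of drugs, risk factors improve the discriminatory performance of standard clinical prediction models". Hypothesis 3A beneath it is a different kind of statement: "Development of metabolic syndrome in cancer patients depends of genetic determinants and toxic effects of antitumor therapy".

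The Analysis of objectives text then gives, under the label Aim 3:

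- crude odds ratios with 95% confidence intervals and Wald tests; of the odds ratios it says "This will be done by univariate conditional logistic regression, to account for the matched design";
- a screen: "Exposures for which the P-value is less than 0.25 in univariate analysis will be entered into a multivariate conditional logistic regression model";
- one final model: "Backward stepwise regression procedures will be used to develop the final multivariate model and possible interactions will be examined";
- a check of that model: "The fit of the model will be assessed by the logistic regression diagnostics procedure";
- haplotypes and multilocus genotype groups where feasible.

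The Sample Size paragraph bases the aims on a "longitudinal assessment of 400 patients with ALL/NHL", and mentions potentially 2100 survivors to be treated at the rehabilitation centre in 2018-2021.

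**The concern.** A gain in discrimination is a contrast between two models. It needs a standard clinical model, the same model with the new predictors added, and a measure such as the AUC for each. The Aim 3 analysis has none of the three. What it specifies is a search for associated exposures, which suits Hypothesis 3A.

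At stake is one of the three specific aims. The study could report significant odds ratios under an aim about better prediction, and readers could take them as evidence that genotype or dose data improve on clinical information. The planned output could not support or refute that.

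**Working it through.** **1. Aim against analysis.** The protocol states no AUC, effect size or power, so there is no figure to reproduce. The check is a comparison of texts.

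| Needed for Aim 3 | In the Aim 3 analysis |
|---|---|
| A defined standard clinical model | None named. The screen and backward selection apply to all exposures, and no predictor is stated to be forced in, so clinical predictors can drop out. |
| An extended model compared with it | None. There is one final model. |
| A discrimination measure | None. Fit diagnostics assess fit. Haplotypes and multilocus groups define predictors. |

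The Exploratory Aim text refers back to the same regression, and no other section supplies the comparison. Conditional logistic regression adds a difficulty: it conditions out the set-specific intercepts and the main effects of matching factors, so it gives no absolute risk and no ordinary cohort AUC.

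**2. Can the odds ratio stand in for the gain?** Every input here is an assumption except the sample sizes of 400 and 2100: metabolic syndrome prevalence 20%, one SNP in Hardy-Weinberg proportions with allele frequency 0.30, independent of a normally distributed clinical score, unmatched logistic model.

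Hand calculation for a per-allele odds ratio of 1.4:

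- SD of the allele count: √(2 × 0.30 × 0.70) = 0.648. Log odds ratio per SD: ln(1.4) × 0.648 = 0.218.
- Binormal approximation: AUC = Φ(d/√2), with d₁ = √(d₀² + 0.218²).
- Base AUC 0.70: d₀ = √2 × Φ⁻¹(0.70) = 0.742, d₁ = 0.773, new AUC 0.708, gain 0.008.
- Base AUC 0.60: d₀ = 0.358, d₁ = 0.419, gain 0.017.
- Base AUC 0.80: d₀ = 1.190, d₁ = 1.210, gain 0.004.
- Approximate crude Wald power: Φ(0.218 × √(N × 0.2 × 0.8) − 1.96). At N = 400 this is Φ(1.744 − 1.96) = 0.41; at N = 2100, Φ(3.997 − 1.96) = 0.98.

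A simulation of 1,000,000 patients for the gain, with Wald power adjusted for the clinical score, agrees:

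| Odds ratio | Base AUC | Gain in AUC | Power, N = 400 | Power, N = 2100 |
|---|---|---|---|---|
| 1.3 | 0.70 | 0.005 | 26% | 86% |
| 1.4 | 0.70 | 0.008 | 40% | 97% |
| 1.5 | 0.70 | 0.012 | 54% | over 99% |
| 1.4 | 0.60 | 0.017 | – | 98% |
| 1.4 | 0.80 | 0.004 | – | 95% |

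For odds ratio 1.4 and base AUC 0.70, the gain stays at 0.008 for prevalence 10% to 30%, and is 0.004 to 0.009 for allele frequency 0.10 to 0.40. Five such SNPs together raise the AUC by 0.036 (0.694 to 0.730).

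The same odds ratio, with almost the same power at 2100, therefore goes with a fourfold range of gain (0.017/0.004), set by a base model the plan never fits. A set of predictors may add little or a material amount, and the planned output does not show which.

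**The case against.** The strongest reply is that the label is unreliable. The Exploratory Aim text attributes the multiple regression described above it to Aims 1 and 2, yet the only multiple regression above it stands after the Aim 3 label. If the label is misplaced, the stepwise text is the association plan, and the discrimination step is merely undescribed, which a statistical analysis plan could supply. Nothing in the text forbids adding a c-statistic either. This does not rescue the plan: the label is explicit, and on either reading no section contains the comparison that Aim 3 needs. An analysis plan that followed the labelled text faithfully would still not answer the aim.

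Two further points stand in part. First, the protocol ties its aims to 400 patients, where an odds ratio of 1.4 is significant in only about 40% of studies, so a clearly significant odds ratio with a tiny gain is more typical of 2100. The dependence of the gain on the base model holds at any sample size. Second, calculations with one or five SNPs, all truly associated, understate the overfitting, because Appendix 1 lists 23 SNPs. That is a fair correction to the cost, taken up under the fix, and it strengthens the case for an optimism correction.

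**Conclusion.** The concern holds. The analysis fixed under Aim 3 targets association and cannot deliver the quantity the aim names. This follows from the text alone and needs no simulation. The numbers only show that odds ratios are no substitute; they rest on assumed prevalence, odds ratios, allele frequencies and base AUCs, and on an unmatched model, whereas the plan is conditional. It should be fixed: a specific aim has no analysis that answers it, and the repair is cheap.

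**What to change.** In the Aim 3 analysis:

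- Pre-specify a standard clinical base model with its predictors forced in, and state which risk factors belong to it and which are being added.
- Add the genetic predictors, drug doses and further risk factors, and report the change in AUC or C-statistic with a 95% CI, corrected for optimism by bootstrap or cross-validation of the whole model-building procedure.
- Estimate the AUC in the unmatched cohort, or account for the matching.
- Keep the odds-ratio analysis for Hypothesis 3A.

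If the comparison will not be done, reword Aim 3 as an association aim and make no claim about discrimination. That costs nothing but gives up the question.

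The comparison itself needs modest extra programming, on data already collected if the base model uses them; the protocol does not yet identify that model. The statistical price is imprecision and a smaller, honest estimate. On the assumptions above (base AUC about 0.70, true odds ratios 1.4):

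| Added predictors | N | Apparent gain | Gain in new patients |
|---|---|---|---|
| 5 SNPs, all associated | 400 | 0.047 (SD 0.021) | 0.026 |
| 5 SNPs, all associated | 2100 | 0.039 (SD 0.009) | 0.034 |
| All 23 SNPs, 5 associated, no selection | 400 | about 0.087 | slightly below zero (−0.004 to −0.008 in repeated runs) |
| All 23 SNPs, 5 associated, no selection | 2100 | about 0.047 | about 0.03 |

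For a single SNP, the estimated gain has SD 0.011 at 400 patients around a true 0.008 (SD 0.004 at 2100). At 400 patients the added predictors should therefore be few and pre-specified, and the optimism correction is essential.

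### The Exploratory Aim defines endothelial dysfunction partly by arterial rigidity, so an association driven by wall stiffness would be reported as endothelial

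*Protocol*

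**What the plan says.** Under Analysis of objectives, the Exploratory Aim applies multiple regression with metabolic syndrome as the outcome. One set of predictors is "biomarker levels (HOMA index, triglyceridemic"). The other is "endothelial dysfunction (rigidness of arteries and positive biomarkers) with metabolic syndrome in cancer treated patients". That parenthesis is the only definition of endothelial dysfunction in the protocol.

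The Evaluation section lists what is measured:
- Stiffness and pressure indices: "CAVI and ABI pulse wave velocity will be non-invasively measured by using the SphygmoCor VaSera VS-1500N".
- A waveform recording: "Arterial pressure waveforms will be recorded with a strain gauge pressure sensor placed lightly over the radial artery before and after" a six-minute activity.
- Imaging: "An echocardiogram and ultrasound will be performed to assess cardiac function".
- Blood: "Biomarker analysis will be completed by Laboratory of Dmitry Rogachev National Medical Research Center". The assays are not named there.

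Under Objectives, Hypothesis 1 B of Secondary Aim 1 uses the same term: "Endothelial dysfunction as a clinical component of metabolic syndrome is responsible for cardio-vascular abnormalities in cancer survivors".

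**The concern.** The label and the measurement do not match. CAVI and pulse wave velocity describe how stiff the arterial wall is, and ABI is an ankle-to-arm pressure ratio. None of them records how the endothelium responds to a stimulus. Stiffness also changes with growth. The survivors are aged 15 or younger and are stratified by survival time (1-4, 5-9, and 10 years or more), so age and body size will differ widely between them.

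If stiffness is associated with metabolic syndrome in this cohort, the association could reflect age or body size, or a change in the wall that does not involve the endothelium. Under the definition as written it would still be reported as a finding about endothelial dysfunction. A reader would then take it as support for the protocol's statements about the endothelium.

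**Working it through.** No arithmetic applies. The protocol attaches no figure to this construct, so the check compares definition, measurement and use.

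1. **Definition (Analysis of objectives, Exploratory Aim).** There are two parts: arterial rigidity and positive biomarkers. The text gives no cut-off and no rule for combining them.

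2. **Measurements that could supply the rigidity part (Evaluation).** These are CAVI and pulse wave velocity, both wall-stiffness indices. ABI is a pressure ratio and belongs to neither part without further explanation.

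3. **Measurements that could supply an endothelial response (Evaluation).** The echocardiogram and ultrasound are assigned to cardiac function. The radial waveform is recorded before and after activity, so it is a response measure of a kind. However, the protocol does not call it an endothelial test or say how it is scored, and the definition in step 1 refers to rigidity, not to a response.

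4. **Measurements that could supply the biomarker part.** Blood is drawn for biomarkers, but no endothelial marker is named. The two biomarkers named in the Exploratory Aim, HOMA and triglycerides, are metabolic and are listed apart from endothelial dysfunction. The positive biomarkers are therefore probably a different set, which may include endothelial markers.

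5. **Does the problem depend on how the parts are combined?** There are three possible readings:
   - *Separate predictors under one heading:* a coefficient for CAVI or pulse wave velocity is still reported as endothelial.
   - *Either part suffices:* a child with stiff arteries and negative markers counts as having endothelial dysfunction.
   - *Both parts required:* a child with positive markers and normal stiffness counts as free of it.

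   The rigidity part affects the endothelial label under all three, so the finding does not need a single composite to be assumed.

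6. **Is growth already handled?** The Exploratory Aim refers back to a regression plan for Aims 1 and 2. The only multivariable regression described stands under Aim 3. There, exposures enter if P is below 0.25 in univariate analysis and are then subject to backward elimination. Neither text commits to keeping age or height in the model. Height and blood pressure are measured (Evaluation), and age is known from eligibility.

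The distinction between wall stiffness and endothelial function, and the dependence of stiffness on age and body size, are general measurement knowledge. The protocol does not state them.

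**The case against.** The strongest reply is that the definition includes biomarkers, that these may well be endothelial, and that their names, cut-offs and combining rule are matters for a statistical analysis plan that is not shown. This stands in part. A reader might infer that endothelial dysfunction is scored from rigidity alone and that the study measures something else entirely. The text does not support that, because the biomarker part is in the definition and its content is unknown. Nor does the text establish a single composite variable; the parenthesis may simply list the measurements considered. What the reply does not remove is the stated rule that rigidity counts as endothelial dysfunction.

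A second reply is that the regression has metabolic syndrome as its outcome, whereas Hypothesis 1 B concerns cardiovascular abnormalities. This is correct. It would be tempting to say that the regression gives a false test of Hypothesis 1 B, or that rigidity makes the hypothesis true by construction. The protocol supports neither: this model does not test that hypothesis, and the cardiovascular abnormalities are not defined. The link is only that the same term is used and no other definition is offered.

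A third reply is that multiple regression is already planned and that covariate lists belong in the analysis plan. Conditional logistic regression for a matched design, if used here, could also deal with age. But the matching factors are not stated, and the selection procedure does not secure age or height.

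Finally, routine adjustment for blood pressure would be unsound. Raised blood pressure is ordinarily a component of metabolic syndrome (the protocol gives no component list), so such a model would condition on part of its own outcome. That objection stands, and it limits the fix.

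**Conclusion.** The point holds in a limited form. The protocol writes arterial rigidity into its definition of endothelial dysfunction, the rigidity measures are wall-stiffness indices, and no endothelium-dependent test is described. An association driven by that part would be mislabelled.

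The consequence is confined to exploratory conclusions and to secondary conclusions that reuse the term. Specific Aims 1 to 3 are untouched. No numerical size can be given. An attenuation figure would need a correlation between stiffness and endothelial function that the protocol does not supply, and it would have to treat stiffness as the only proxy, contrary to the definition.

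The conclusion rests on two pieces of general knowledge: CAVI and pulse wave velocity index wall stiffness, and stiffness in children varies with age and body size. It does not rest on any assumption about which biomarkers are assayed or how the parts are combined.

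**What to change.** In the Exploratory Aim:

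- Replace the two-part definition by three separately named sets of predictors: arterial stiffness (CAVI, pulse wave velocity), ABI, and the endothelial blood biomarkers, listed by name.
- Keep age and height in any model that contains a stiffness term, whatever the selection procedure does. Add blood pressure only in a sensitivity analysis, and say why.
- Report CAVI and pulse wave velocity as stiffness. Base statements about endothelial dysfunction, including any made under Hypothesis 1 B, on the endothelial biomarkers only. If the blood panel contains no such marker, make no endothelial claim.

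Height, blood pressure and age are already available, so the change needs no new measurement, provided the planned panel includes endothelial markers. The cost is a few more model terms and a narrower endothelial claim.
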